4.1.1. Definition of Baseline

Unless specified otherwise, baseline is defined as the last non-missing measurement recorded on or before the randomization visit (Visit 2), prior to the first dose of intervention, which in most cases will be the measurement recorded at Week 0 (Visit 2). For the safety related parameters, the definition of baseline and postbaseline are specified in Table EKBC.4.2.

Study Period/	Particinant Population	Baseline Observations	Postbaseline Observations
Analysis Type	i articipant i opulation	Daschile Observations	i ostbasenne observations
1.1) Treatment-	All randomized participants	The baseline period is	Starts at or after the first
Emergent Adverse	who are exposed to at least	defined as the start of	dose of study drug and ends
Events (SS)	1 dose of study drug	screening and ends prior to	at the conclusion of the
		the first dose of study drug.	study period.
1.2) Treatment-	All randomized participants	Baseline will be all	Postbaseline will be defined
Emergent Abnormal	who are exposed to at least	scheduled and unscheduled	as above (1.1). All
Labs and Vital Signs	1 dose of study drug who	measurements recorded	scheduled and unscheduled
(SS)	have a normal baseline	during the baseline period as	measurements will be
	(with respect to the direction	defined above (1.1).	included.
	being analyzed) and a post-		
	baseline observation		
1.3) Change from	All randomized participants	The last scheduled non-	Postbaseline will be defined
Last Baseline to each	who are exposed to at least	missing assessment	as above (1.1). Only
postbaseline week	1 dose of study drug and	recorded prior to the first	scheduled visits will be
and to last	have a baseline and at least	dose of study treatment	included. The early
postbaseline for Labs,	1 post-baseline observation	during the baseline period	discontinuation visits are
Vital Signs (SS)		defined above (1.1).	considered scheduled visits.

 Table EKBC.4.2.
 Baseline and Postbaseline Definitions for Safety Analyses

Abbreviations: ED = early discontinuation; SS = safety set.

Note: for the continuous analysis of clinical laboratory tests, unscheduled measurements are excluded from analysis to reduce bias. The early discontinuation visits are considered scheduled visits.

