2.2. Background

2.2.1. Introduction to Lp(a)

Lp(a) is an atherogenic lipoprotein consisting of an LDL-like particle linked via a disulfide bond to apo(a).

Apo(a) is a protein found in new-world monkeys, great apes, and humans (Utermann 1989). The protein, encoded by the LPA gene, includes 10 unique units of kringle IV repeats; the first and third through tenth are present in single copies while the second is present in variable copy numbers (1 to <50). Additionally, the protein includes a kringle V and a protease-like domain that is not biologically active (Dubé et al. 2012; Kronenberg and Utermann 2013; Tsimikas 2017).

[figure not shown]

Figure 1. Representation of Lp(a) particle.

Abbreviations: Apo(a) = apolipoprotein(a); ApoB = apolipoprotein b; LDL = low-density lipoprotein.

Lp(a) contains oxidized phospholipids. Plasma levels of Lp(a) are genetically determined. Single-nucleotide polymorphisms (SNPs) of the LPA gene are associated with higher or lower Lp(a) levels; for example, rs10455872 and rs3798220 are associated with increased Lp(a) (Clarke et al. 2009; Li et al. 2011). Additionally, the number of kringle IV2 repeats determines protein size, which is inversely proportional to plasma concentration and mass of Lp(a); larger apo(a) size is associated with lower concentrations of Lp(a). Despite this genetically induced variability in Lp(a) concentrations between individuals, intra-patient variability in Lp(a) is low and is not thought to be materially impacted by diet, environmental factors, or exercise (Schmidt et al. 2016). However, apo(a) is an acute-phase reactant, and Lp(a) increases, for example, after surgery, myocardial infarction, and infection (Maeda et al. 1989; Min et al. 1997; Noma et al. 1994).

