5.2. Exclusion Criteria

Participants are excluded from the study if any of the following criteria apply:

Medical Conditions

9. Have a history or presence of an underlying disease, or surgical, physical, medical, or psychiatric condition that, in the opinion of the investigator, would potentially affect participant safety within the study or interfere with participating in or completing the study or with the interpretation of data.

10. Any of the following, or other events indicating unstable medical condition in the opinion of the investigator, within 3 months of Visit 1:

- a. major surgery
- b. coronary, carotid, or peripheral arterial revascularization
- c. stroke or transient ischemic attack
- d. myocardial infarction or unstable angina
- e. acute limb ischemia.
- 11. Have, in the 6 months prior to Visit 1, uncontrolled Type 1 or Type 2 diabetes, defined as an episode of ketoacidosis or hyperosmolar state requiring hospitalization, or have a hemoglobin A1c (HbA1c) ≥8% at Visit 1.
- 12. Have uncontrolled hypertension with a resting blood pressure ≥160 mm Hg systolic and/or ≥100 mm Hg diastolic at Visit 1; a repeat measure is allowed.
- 13. New York Health Association Class III or IV heart failure or last known left ventricular ejection fraction <30%.
- 14. Active or acute infection requiring systemic antiviral or antimicrobial therapy that will not be completed prior to Visit 2.
- 15. Malignancy within 5 years, except for basal or squamous cell carcinoma of the skin or carcinoma in situ of the cervix that has been successfully treated.
- 16. Recent history of, or current drug or alcohol abuse in the opinion of the investigator.
- 17. Have 2 or more clinically significant or severe drug allergies, or severe post-treatment hypersensitivity reactions, including, but not limited to
 - a. erythema multiforme major
 - b. linear immunoglobulin A dermatosis
 - c. toxic epidermal necrolysis
 - d. exfoliative dermatitis.
- 18. Hypersensitivity to the active substance or to any of the excipients.
- 19. Have a current infection with hepatitis B virus (HBV), that is, positive for hepatitis B surface antigen (HBsAg) and/or PCR positive for HBV deoxyribonucleic acid (DNA) (Section 8.2.5).
- 20. Have a current infection with hepatitis C virus (HCV), that is, positive for HCV ribonucleic acid (RNA) (Section 8.2.6).
- 21. Have human immunodeficiency virus (HIV) infection.

Prior/Concomitant therapy

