9.3.2. Primary Endpoint/Estimand Analysis

The primary efficacy assessment, guided by the efficacy estimand, will be conducted using the EAS for the primary endpoint.

For the efficacy estimand, the hypothetical strategy is used to handle the intercurrent events of permanent discontinuation of intervention. The "treatment-regimen" estimand, which represents the efficacy regardless of treatment discontinuation, may also be used to compare the primary efficacy of LY3473329 doses with placebo. The analysis guided by the "treatment-regimen" estimand will use the FAS.

The primary efficacy comparison will be based on the contrast between each treatment group of LY3473329 and placebo for the mean percent change of Lp(a) from randomization at Visit 2 to Week 12 at Visit 7.

The primary analyses model will be MMRM as described in Section 9.3.1. The Lp(a) will be log transformed before statistical analyses, and then back-transformed to present percentage change from baseline. Treatment comparisons will be performed at the full significance level of 0.05. Additional covariates may be added, and this analysis will be detailed in the SAP.

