4.1.2. Analysis methods

4.1.2.1. Analysis method for efficacy estimand

Unless otherwise specified, the primary endpoint, secondary endpoints, and exploratory endpoints will be analyzed according to the efficacy estimand, which represents the efficacy had participants adhered to the randomized treatment without initiating Lp(a) modifying medications. Considered Lp(a) modifying medications are listed in Table EKBC.4.3. The assessment of efficacy measurements guided by the efficacy estimand will be conducted using the EAS (Section 3).

Table EKBC.4.3. Lp(a) Modifying Medica	tions
--	-------

Category	Medication
Lp(a)-Altering therapies	 statins PCSK9 inhibitors prescription-dose niacin mipomersen testosterone, estrogens, anti-estrogens, progestins, selective estrogen receptor modulators, or growth hormone
Excluded Treatment Medical Devices, and/or Procedures	 lipid apheresis any investigational drug, biological agent, or device other than study provided investigational product

A restricted maximum likelihood-based, mixed-effect model repeated measures (MMRM) analysis will be used to analyze continuous longitudinal endpoints. All the longitudinal observations at each scheduled postbaseline visit will be included in the analysis. The MMRM model will include the fixed class effects of treatment group (LY 10 mg, LY 60 mg, LY 240 mg, and placebo), strata (country and baseline Lp(a) stratum [<275 nmol/L, \geq 275 nmol/L as measured by the apo(a) assay]), visit, and treatment-by-visit interaction, as well as the continuous baseline value. An unstructured covariance structure will be used to model the within-participant errors. Significance tests will be based on LS means and Type III tests. If this analysis fails to converge, the following covariance structures will be tested in order:

- 1. Toeplitz with heterogeneity
- 2. autoregressive with heterogeneity
- 3. compound symmetry with heterogeneous variances
- 4. Toeplitz
- 5. autoregressive, and
- 6. compound symmetry without heterogeneous variances.

The first covariance structure that converges will be used. The Kenward-Roger approximation will be used to estimate denominator degrees of freedom.

If the data does not warrant the MMRM model, then an ANCOVA model with treatment group, strata, and the continuous baseline value will be used to analyze the continuous endpoint. Data for participants with missing values at Week 12 will be imputed using the multiple imputation

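### hsCRP and ApoB are adjusted for one pre-dose value although two are collected; adding the Visit 1 value as a covariate could gain precision at almost no cost

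*SAP*

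**What the plan says.** For efficacy, SAP 4.1.1 states that "baseline is defined as the last non-missing measurement recorded on or before the randomization visit (Visit 2), prior to the first dose of intervention" and expects this to be the Week 0 sample in most cases. An earlier value such as Visit 1 therefore serves only as a fallback. Protocol 9.3.2 likewise measures the primary change "from randomization at Visit 2 to Week 12 at Visit 7".

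The MMRM in SAP 4.1.2.1 contains treatment, strata, visit and treatment by visit, "as well as the continuous baseline value". It has no other pre-dose covariate.

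The Schedule of Activities (Protocol 1.3) has hsCRP and ApoB drawn at both Visit 1 and Visit 2. Visit 1 is at most three weeks before randomization, and dosing starts at Visit 2.

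The protocol leaves room for more adjustment. Section 9.3.2 says of the primary model: "Additional covariates may be added, and this analysis will be detailed in the SAP". Section 9.3.3 gives the same latitude for the secondary endpoints. The SAP does not use it.

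SAP 4.4.2 declares superiority on each secondary hypothesis at p below 0.05. The sample size sections (Protocol 9.5, SAP 5) cover only Lp(a).

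**The concern.** One reading of a variable marker is an imperfect measure of a participant's usual level. When a second pre-dose reading is already in the database, a model that uses both normally predicts the Week 12 value at least as well as a model that uses one, and the treatment contrast is then estimated with a smaller standard error.

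This matters most for hsCRP. It is tested at 0.05 with no stated power, and the 10 mg arm is expected to have only about 30 completers. ApoB is in the same position, and its case rests on ordinary measurement precision alone. What is at stake is the width of the confidence intervals; the estimates themselves remain valid.

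**Working it through.** **1. The plan's own figures, to see whether the primary test is touched.**
- Completers: 233 × 1/7 × 0.9 = 29.96 and 233 × 2/7 × 0.9 = 59.9. These match the stated 30 and 60.
- 30 versus 60, SD 20, difference 60: SE = 20 × √(1/30 + 1/60) = 4.47, and 60/4.47 = 13.4.
- 60 versus 60: SE = 20 × √(2/60) = 3.65, and 60/3.65 = 16.4.
- Power is above 99.99% in both cases, so the stated figure of more than 99% is reproduced.
- The SD would have to rise from 20% to about 63% (30 versus 60) or 77% (60 versus 60) before power fell to 99%. On the documents' assumptions, the handling of baseline cannot matter for the primary Lp(a) test.

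**2. Gain from a second covariate.** On the log scale with unit variances, let c be the correlation of Visit 1 with Visit 2, b that of Visit 2 with Week 12, and a that of Visit 1 with Week 12. The documents give none of these, so all are assumptions.
- Residual variance with Visit 2 alone: 1 − b².
- Proportional reduction from adding Visit 1: (a − bc)² / [(1 − c²)(1 − b²)].
- With all three equal to r, this simplifies to [r/(1 + r)]².
- The SE changes by the factor √(1 − reduction).

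| c, b, a | Variance reduction | SE reduction |
|---|---|---|
| 0.5, 0.5, 0.5 | 11% | 5.7% |
| 0.6, 0.6, 0.6 | 14% | 7.3% |
| 0.7, 0.7, 0.7 | 17% | 8.9% |
| 0.8, 0.8, 0.8 | 20% | 10.4% |
| 0.6, 0.55, 0.50 | 6.5% | 3.3% |
| 0.7, 0.60, 0.55 | 5.2% | 2.6% |
| 0.8, 0.70, 0.65 | 4.4% | 2.2% |
| 0.7, 0.60, 0.45 | 0.3% | 0.1% |
| 0.7, 0.60, 0.42 | 0% | 0% |

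Example, sixth row: (0.55 − 0.42)² / (0.51 × 0.64) = 0.0169/0.3264 = 5.2%. The last row has a = bc (0.7 × 0.6 = 0.42). There Visit 1 carries no information beyond Visit 2, and the gain vanishes.

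**3. Does infection near baseline drive this?** Assume r = 0.6, log SD 1, 60 per arm, and a 5-fold hsCRP rise in 5% of participants at one visit.
- The rise adds (ln 5)² × 0.05 × 0.95 = 0.123 to the variance at that visit.
- Visit 2 alone, no rise: residual variance 1 − 0.36 = 0.64, SE = √(0.64 × 2/60) = 0.146.
- Visit 2 alone, rise at Visit 2: 1 − 0.36/1.123 = 0.679, SE 0.150.
- Both covariates, no rise: 1 − 2 × 0.36/1.6 = 0.55, SE 0.135.
- Both covariates, rise at one visit, whichever it is: 1 − 0.36 × (1.123 + 1 − 1.2)/(1.123 − 0.36) = 0.564, SE 0.137.

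The infection scenario moves the SE by about 0.004 (0.146 to 0.150). The second covariate moves it by about 0.011 (0.146 to 0.135) with no infection at all. Simulation under the same assumptions (4,000 trials) agrees with these standard errors to within simulation error and shows no bias in the treatment contrast.

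**The case against.** **A single baseline is a legitimate choice.** Protocol and SAP agree on it, the model already adjusts for it, and the protocol only permits further covariates. That stands, and it is why this is not an error.

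**The gain may be nil.** This also stands. If the correlation with Week 12 decays steadily with time, Visit 1 adds nothing.

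**Visit 1 may be the worse sample.** Exclusion 14 removes only "Active or acute infection requiring systemic antiviral or antimicrobial therapy that will not be completed prior to Visit 2", so an infection may still be under treatment at Visit 1. This tells against averaging the two visits. It has little force against a separate covariate, because the model estimates its weight: in step 3 the SE with both covariates is 0.137 when only Visit 1 carries the rise, against 0.146 for Visit 2 alone.

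**A stronger reading is tempting.** Protocol 2.2.1 says that "apo(a) is an acute-phase reactant, and Lp(a) increases, for example, after surgery, myocardial infarction, and infection", so a reader might infer that infections resolving near Visit 2 distort the results for all three markers. The documents do not support that:
- Any such rise occurs before the first dose and is balanced by randomization in expectation.
- The documents give no acute-phase basis for ApoB.
- The same protocol section describes variation in Lp(a) within a person as low.
- Exclusion 10 already removes major surgery and myocardial infarction within three months of Visit 1, and exclusions 9 and 26 give the investigator further discretion.

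**Conclusion.** The point holds as a low-priority, nearly free gain in precision for hsCRP, and for ApoB on measurement grounds only. The expected reduction is about 0% to 20% in residual variance, or 0% to about 10% in SE. It rests entirely on assumed correlations, and on treating the Week 12 contrast as an analysis of covariance on the log scale.

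Three further inferences should not be drawn. The between-arm estimates are not biased. The primary Lp(a) test is not at risk. The change would not remove any shift in within-arm percent change caused by an unusual Visit 2 value, because Visit 2 remains the reference.

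**What to change.** In SAP 4.1.2.1, for hsCRP and ApoB:
- Prespecify the log Visit 1 value as a second continuous covariate beside the log Visit 2 baseline. Do not average the two.
- Keep Visit 2 as the reference for percent change, so that the endpoint definition is unchanged.
- State a rule for a participant who lacks either pre-dose value, for example imputing the missing covariate from the other one without regard to arm. Without a rule, the fallback in SAP 4.1.1 would enter the same number twice.
- State firmly that both markers are analyzed on the log scale. SAP 4.1 says so for percent-change endpoints, whereas SAP 4.4.2 leaves it open for secondary endpoints.

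The cost is a few lines of SAP text and one model degree of freedom. No new samples are needed, and the protocol already allows the added covariate. The text should be fixed before unblinding. The Lp(a) models can stay as they are.

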1.3. Schedule of Activities (SoA)

Period I - Optional Pre-screening: The study includes an optional prescreening visit (Visit 601) as a simple way for sites to determine whether participants meet Lp(a) criteria, as assessed by a central laboratory assessment, before the full screening activities are initiated at Visit 1. If the participant has not had Lp(a) measured before or is unknown, the prescreening visit should be completed. The prescreening visit can be conducted at the study site, or remotely, for example, at a mobile healthcare or alternate laboratory. The prescreening determination of Lp(a) will be described in an appropriate informed consent form (ICF). Informed consent for the prescreening activities will be obtained, a participant identification number will be assigned, and sample for the Lp(a) prescreening laboratory test will be obtained. The optional prescreening visit can be repeated 1 time (no more) per participant if the investigator believes the participant would meet criteria at a later time, with a minimum of 4 weeks between visits. Repeated sampling in the prescreening visit will not require re-consenting or assignment of a new participant identification number. Note: If the optional prescreening is opted for, central laboratory testing for Lp(a) is still required as part of the screening procedures conducted at Visit 1. Participants with insufficiently high Lp(a) at Visit 1 will not be eligible for enrollment, despite their values in prescreening. A prescreening visit occurring longer or shorter than 3 weeks (21 days) from screening will not be considered a protocol deviation.

Period II - Screening: Visit 1 procedures may be conducted over more than 1 day as long as all activities are completed prior to Visit 2.

Period III - Treatment Period: All procedures (screening and baseline) need to be completed prior to the first dose of study intervention. For an early discontinuation (ED) from the study intervention that occurs before the last visit in treatment period, see the activities listed for ED in this table.

Period IV - Post Treatment Follow-Up: After completing Visits 7 and 8, there will be a follow-up Visit 801 approximately 4 weeks after discontinuing study intervention. This 4-week duration is greater than 5 times the effective half-life of the drug and thus will support adequate drug washout.

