Additionally, laboratory assessments at Visit 801 will provide information about the pharmacodynamic (PD) offset of study intervention on Lp(a).

	Period I - Pre- Screening	Period II - Screening		Period III - Treatment Period							Period IV - Post- Treatment Follow-Up	
Visit number	601	1	2	3	4	5	6	7	8	ED	801	
Weeks from randomization	≤6	≤3		1	2	4	8	12	12*	_	4 weeks from last dose	*Visit 8 occurs 1-3 days after final dose
Visit interval tolerance (days)	See Section 1.3	_	_	±2	±3	±3	±4	±4	_	_	±5	
Fasting Visit		X	X	X	X	X	X	X				If a participant arrives not fasted, schedule the laboratory draw for another date. See Section 5.3.1.
Pre-Screening informed consent	X											
Informed consent		X										The ICF must be signed before any protocol- specific tests or procedures are performed. See Appendix 10.1.3 for additional details.
Inclusion and exclusion criteria, review and confirm		X	X									Inclusion and exclusion criteria should be confirmed-prior to drug assignment and administration of first dose of study intervention.
Demographics		X										Includes year of birth, sex, ethnicity (where permissible), and race.
Preexisting conditions and medical history, including relevant surgical history		X										All conditions ongoing and relevant past surgical and medical history should be collected.
Prespecified medical history (indication and history of interest)		X										Prespecified medical history includes indication and history of cardiovascular events.
Prior treatments for indication		X										Relevant prior therapies include, but are not limited to, lipid lowering medications.
Substance use (alcohol, caffeine, and tobacco use)		X										
Concomitant medications		X	X	X	X	X	X	X		X	X	Additional data will be collected for medications of interest.

	Period I - Pre- Screening	Period II - Screening		Per	riod I	II - Ti	reatm	nent P	eriod		Period IV - Post- Treatment Follow-Up	
Visit number	601	1	2	3	4	5	6	7	8	ED	801	
Weeks from randomization	≤6	≤3		1	2	4	8	12	12*		4 weeks from last dose	*Visit 8 occurs 1-3 days after final dose
Visit interval tolerance (days)	See Section 1.3		_	±2	±3	±3	±4	±4	-	_	±5	
Fasting Visit		X	X	X	X	X	X	X				If a participant arrives not fasted, schedule the laboratory draw for another date. See Section 5.3.1.
AEs	X	X	X	X	X	X	X	X		X	X	Any events that occur after signing the informed consent are considered AEs as defined (Section 10.3). Additional data are collected for certain AEs.
Physical Evaluation												

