2.1. Multiplicity Adjustment

Treatment comparisons will be performed for the primary objective at the full significance level of 0.05. No multiplicity adjustments will be made for the analysis of secondary and exploratory objectives.

3. Analysis Sets

This table defines the analysis population and datasets for the purposes of analysis.

Population	Description
Screened	All participants who sign the ICF.
Randomized	All participants who are randomly assigned to a treatment arm.
Efficacy Analysis Set (EAS)	Data obtained during treatment period from all randomly assigned participants who are exposed to at least 1 dose of double-blind study treatment. Excludes data after discontinuation of study drug or initiation of Lp(a) modifying medication.
Full Analysis Set (FAS)	Data obtained during the treatment period from all randomly assigned participants who are exposed to at least 1 dose of intervention, regardless of adherence to intervention or initiation of Lp(a) modifying medication.
Safety Analysis Set (SS)	Data obtained during the treatment period plus safety follow-up from all randomly assigned participants who are exposed to at least 1 dose of intervention, regardless of adherence to intervention or initiation of Lp(a) modifying medication.

Abbreviation: ICF = informed consent form.

4. Statistical Analyses

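### As written, the SAP's last-postbaseline change for vital signs and most labs uses the post-washout Visit 801 value, so that one safety summary would dilute a reversible drug effect and mix off-drug with on-drug endpoints

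*SAP*

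**What the plan says.** Four statements combine.

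- **SAP 4.1.1, Table EKBC.4.2, row 1.3.** The analysis is change from last baseline to every postbaseline week and also to the last "postbaseline for Labs" and vital signs, in the Safety Analysis Set. Postbaseline is defined "as above (1.1). Only" scheduled visits are used, and early discontinuation (ED) visits count as scheduled.
- **Row 1.1 of the same table.** The window that row 1.3 borrows opens at first dose and closes "at the conclusion of the" study period. It has no cut at last dose, Visit 7 or ED.
- **SAP Section 3, Safety Analysis Set.** "Data obtained during the treatment period plus safety follow-up from all randomly assigned participants" with at least one dose. Follow-up data are therefore in the set.
- **Protocol 1.3, Period IV.** After treatment, "there will be a follow-up Visit 801 approximately 4 weeks after discontinuing study intervention". The protocol adds: "This 4-week duration is greater than 5 times the effective half-life of the drug and thus will support adequate drug washout". It also says that "laboratory assessments at Visit 801 will provide information about the pharmacodynamic (PD) offset" of the drug's action on Lp(a).

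The Schedule of Activities marks vital signs, hematology, clinical chemistry, lipid panel, Lp(a), ApoB, plasminogen activity and hsCRP at Visit 801. It does not mark urinalysis, UACR or eGFR there; their last scheduled collection is Visit 7 or ED. Protocol 7.1 sends participants who stop the drug early to an ED visit and then to post-treatment follow-up, if applicable.

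**The concern.** A change to the last postbaseline value in a safety report is usually read as the state at the end of treatment. Under these definitions it is, for most parameters, the state after washout. A drug effect that reverses on stopping would be largely absent from that summary even if it had been present throughout the 12 weeks. The protocol expects reversal for Lp(a): the synopsis says that the effect goes away once the drug is stopped, and Protocol 4.2 gives return to baseline as a purpose of the follow-up visit.

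The summary would also not mean the same thing from one row to the next. Creatinine belongs to the chemistry panel and is drawn at Visit 801, so its last value is off drug. eGFR is not scheduled there, so its last value is on drug for a participant who completes treatment. Nothing in the definition would tell the reader which is which.

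**Working it through.** **1. Which visit supplies the last value.** The documents give no figure for this summary, so the first step is textual. Row 1.3 takes its window from row 1.1 (first dose to the end of the study period). The Safety Analysis Set adds safety follow-up, and Visit 801 is a scheduled visit. For a parameter collected there, the latest scheduled value is the Visit 801 value whenever the participant attends. An ED value is likewise superseded if the participant goes on to Visit 801.

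| Parameter | Scheduled at Visit 801? | Last scheduled value |
|---|---|---|
| Vital signs, hematology, chemistry, lipids, plasminogen activity, hsCRP | Yes | Visit 801 if attended: off drug |
| Urinalysis, UACR, eGFR | No | Visit 7 or ED |

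**2. How much drug is left.** Inputs from Protocol 1.3: Visit 801 is 4 weeks (28 days) after last dose, tolerance ±5 days, and 28 days exceeds 5 effective half-lives. The longest half-life consistent with this is 28/5 = 5.6 days. The fraction remaining at day d is then at most 2^(−d/5.6):

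- day 23: 23/5.6 = 4.1 half-lives, 5.8%
- day 28: 5.0 half-lives, 3.1%
- day 33: 33/5.6 = 5.9 half-lives, 1.7%

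A shorter half-life leaves less.

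**3. What that does to the mean change.** Let q be the share of participants with a Visit 801 value and r the share of the on-drug effect still present then. Suppose those without a Visit 801 value contribute the full on-drug effect. The share retained in the last-postbaseline mean is (1 − q) + q·r. Neither q nor r is given in the documents. With r = 3%, that is, an effect that tracks drug level:

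- q = 100%: 0 + 0.03 = 3%
- q = 90%: 0.10 + 0.027 = 13%
- q = 80%: 0.20 + 0.024 = 22%
- q = 50%: 0.50 + 0.015 = 52%

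Ending the window at Visit 7 or ED would keep essentially all of it.

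**4. Illustration.** The plan's completer numbers reproduce: 233 × 2/7 × 0.9 = 59.9, against 60 stated for each larger arm. Take 60 versus 60, two-sided alpha 0.05, and an assumed reversible shift of 0.5 SD.

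- At Visit 7 the noncentrality is 0.5 × √30 = 2.74 and power is 78%.
- At last postbaseline with q = 90% and r = 3%, the shift is 0.5 × 0.127 = 0.0635 SD, the noncentrality is 0.35, and power is about 6% counting both tails, close to the 5% alpha level.

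**5. A side effect.** Protocol 5.3.1 requires fasting for Visits 1 to 7, and the Schedule of Activities does not mark Visit 801 as a fasting visit. Last-postbaseline glucose and triglycerides could therefore set a non-fasting value against a fasting baseline.

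**The case against.** A reader might infer that the plan hides any reversible safety effect and so biases the safety conclusion toward no effect. The documents do not support that. On-drug values are visible in several places:

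- Row 1.3 itself also plans change to each postbaseline week. SAP 4.6.4 and 4.6.6 give summaries by nominal visit, as Protocol 9.3.5.1 requires.
- SAP 4.6.6 models selected lab tests during the treatment period, and SAP 4.6.4 applies the repeated-measures model to vital signs.
- Plasminogen activity, where the protocol reports a preclinical lowering, is analysed by MMRM under the efficacy estimand (SAP 4.5), which excludes data after the drug is stopped.
- Treatment-emergent abnormalities use all postbaseline values (SAP 4.1.2.3). The hepatic threshold counts cover the treatment period (SAP 4.6.7.1.1).

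It is also fair that last postbaseline appears only in a definitions table. SAP 4.6.4 and 4.6.6 name no output or test for it, so its weight in reporting is unknown. A last value that includes follow-up does fit a safety estimand covering treatment plus follow-up, and can show whether a change persists. These points limit the consequence; they do not supply the missing on-treatment cut.

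The remaining defence is that the study period is undefined and might mean the treatment period only. That reading would also close row 1.1's adverse-event window at the end of treatment, against the Safety Analysis Set and the safety estimand in SAP 1.1. Where the authors mean treatment only, as in the lab model of SAP 4.6.6, they say so. If treatment only was intended here, row 1.3 still needs to state it.

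**Conclusion.** The definition should be corrected; the severity is minor. For vital signs and most labs, last postbaseline as written is an off-drug value for anyone who attends Visit 801, and for urinalysis, UACR and eGFR it is not.

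The 3% to 6% residual is an upper range at days 28 and 23, on the longest half-life the protocol allows. It describes drug level and carries over to a safety parameter only if that parameter tracks drug level. An effect that outlasts the drug would be diluted less. Attendance at Visit 801 and the 0.5 SD shift are likewise assumptions. The finding concerns this one summary; no bias in the overall safety conclusion has been shown.

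**What to change.** In SAP Table EKBC.4.2, row 1.3, define last postbaseline as the last scheduled value in the treatment period, through Visit 7 or the ED visit. Report change from baseline at Visit 801 as a separate line labelled off-drug follow-up, with a note that the visit is not marked as fasting. Leave rows 1.1 and 1.2 as they are, so that adverse events and treatment-emergent abnormalities still cover follow-up.

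The cost is one table cell and one output label. No new data are needed, and no other analysis changes.
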